# 14.5. Efficacy Analysis

# 14.6. Bioanalytical Analyses

Whole blood samples from participants who received the XT-150 will be analyzed for anti-IL10 antibodies and plasmid DNA using validated assays. Any detection of anti-IL-10 antibodies or plasmid will be described by treatment and timepoint.

# 14.7. Handling of Dropouts and Missing, Unused, and Spurious Data

Every effort will be made to collect all data at specified times. All participants who received any dose of XT-150 study drug but with missing outcome data will nonetheless be included in the Safety Population. Treatment of missing or spurious data will be specified in the SAP.

#### 14.8. Termination Criteria

Withdrawals from the study and from study drug will be summarized in a listing.

# 14.9. Deviation Reporting

Protocol deviations will be summarized by treatment group. Protocol deviations are defined as any variation from the protocol, including enrollment of a participant who did not meet all inclusion and exclusion criteria and failure to perform the assessments and procedures within the required time frame.

## 15. INVESTIGATOR REQUIREMENTS

#### 15.1. Protocol Adherence

The Investigator must adhere to the protocol as detailed in this document and agree that the Sponsor must approve any change to the protocol before seeking approval from the IRB. The Investigator will be responsible for enrolling only those participants who have met the protocol inclusion and exclusion criteria.

## 15.1.1. Investigator or Designee Experience

The Investigator or Investigator's designee is required to be qualified, trained, and experienced in the administration of study drug by intra-articular injection.

## 15.2. Case Report Forms

The CRF will be supplied by the Sponsor or designee for the recording of all information and study data as specified by this protocol. All CRFs must be completed by trained study personnel. The Investigator is responsible for ensuring that the CRF data are entered and completed in a timely manner.

Once all data queries and issues have been resolved for each participant, the Investigator will electronically sign each participant's CRF to attest to the accuracy of the data.

## 15.3. Source Document Maintenance

Source documents are defined as documentation related to original observations and activities of a clinical investigation. Source documents may include, but are not limited to, study progress notes, study- or participant-specific e-mail correspondence, computer printouts, laboratory data, and recorded data from automated instruments. All source documents produced in this study will be maintained by the Investigator and made available for inspections by the Sponsor and by regulatory authorities. The original signed ICF (and any updates, if appropriate) for each participant shall be filed with records kept by the Investigator, and a copy shall be given to the participant.

A telephone call documenting safety and efficacy assessments may be used for participants unable to physically attend follow up visits due to COVID-19 infection or corona virus exposure concerns. Participant responses will be captured in source documents, including circumstances for use of telephone follow up.

# 15.4. Study Monitoring Requirements

An authorized Sponsor representative will conduct site visits to inspect study data, participants' medical records, and CRFs in accordance with International Council for Harmonisation of Technical Requirements for Pharmaceuticals for Human Use (ICH) guidelines, GCPs, and the foreign regulations and guidelines, as applicable. A study monitor will be utilized for monitoring ongoing drug accountability and adherence to protocol procedures.

The Investigator will allow representatives of the Sponsor and regulatory authorities to inspect facilities and records relevant to this study.

# 15.5. Study Completion

The Sponsor requires the following data and materials before a study can be considered complete or terminated:

- Laboratory findings, clinical data, and study test results from Screening throughout the study through Day 270
- CRFs (including data queries) properly completed by appropriate study personnel and signed and dated by the Investigator
- Copies of complete drug accountability records (drug inventory log and an inventory of returned or destroyed clinical material)
- Copies of protocol amendments and IRB/ approval and notification, if appropriate
- A summary of the study prepared by the Investigator (an IRB summary letter is acceptable)

## 16. QUALITY CONTROL AND QUALITY ASSURANCE

Written standard operating procedures (SOPs) will be followed to ensure that the study is conducted and data are generated, documented (recorded), and reported in compliance with the protocol, GCP, and the applicable regulatory requirements. Quality control will be applied to each stage of data handling. Regular monitoring, as defined in ICH GCP, Section 1.8, "The act of overseeing the progress of a clinical trial, and of ensuring that it is conducted, recorded, and reported in accordance with the protocol, SOPs, GCP, and the applicable regulatory requirement(s)", will be conducted throughout the conduct of the study.

The purpose of monitoring is to verify that:

- Rights and well-being of the human participants are protected
- The reported study data are accurate, complete, and verifiable from source documents
- The conduct of the study is in compliance with the currently approved protocol/amendment(s), with GCP, and with the applicable regulatory requirements
- Monitoring is an integral role in the quality control of a clinical trial and is designed to ensure and verify the quality of the study

To fulfill the Quality Assurance requirements of GCP, audits will be conducted to assess and assure the reliability and integrity of a study's quality control systems and recognized standards.

The purpose of an audit is to:

- Ensure participant safety
- Assure compliance to study protocol procedures, regulatory requirements, and SOPs
- Assure data quality

#### 17. PROTECTION OF HUMAN PARTICIPANTS

This study will be conducted in compliance with the ICH Technical Requirements for Registration of Pharmaceuticals for Human Use E6 GCP: Consolidated Guidelines, the ethical principles of the Declaration of Helsinki, Food and Drug Administration (FDA) GCP guidelines, and any additional national or IRB-required procedures, particularly those related to the Corona Virus Disease 2019 (COVID-19) pandemic.

## 17.1. Informed Consent

This study will be conducted in compliance with ICH E6 GCP: Consolidated Guidelines pertaining to informed consent. Participants will give written consent to participate in the study at the first visit, prior to initiation of any study-related procedures, after having been informed about the nature and purpose of the study, participation and termination conditions, risks, and benefits. If a participant is unable to provide written informed consent, the participant's legally acceptable representative may provide written consent, as approved according to institution-specific guidelines. The ICF must be signed and dated by the participant, or the participant's legally authorized representative, prior to study participation. A copy of the ICF must be provided to the participant or the participant's legally authorized representative. If applicable, it will be provided in certified translation for non-English-speaking participants. Signed consent forms must remain in the participant's study file and be available for verification by Sponsor at any time.

## 17.2. IRB Approval

This protocol, the ICF, and all relevant supporting data must be submitted to the IRB for approval. The protocol, ICF, and any advertisement used to recruit study participants must be approved by the IRB. Approval by the IRB of the protocol and ICF must be obtained before the study may be initiated.

The Investigator is responsible for informing the IRB of any changes made to the protocol, and to advise them, at least once a year, about the progress of the study. The Investigator is also responsible for notifying the IRB of any significant AEs or other important events that occur during the study based on the IRB's reporting requirements.

## 18. DATA HANDLING AND RECORD KEEPING

Training sessions, regular monitoring of Investigators by Sponsor-designated personnel, instruction manuals, data verification, crosschecking, and data audits will be performed to ensure the quality of all study data. Investigator meetings will be performed to train Investigators and other study personnel in the appropriate collection of study data. The Sponsor or designee will review and validate study data according to standard procedures.

It will be the responsibility of the Investigator to ensure that the essential documents are available at the Investigator or institutional site. Any or all of these documents may be participant to, and should be available for, monitoring by the Sponsor or inspection by the regulatory authorities as defined in the monitoring plan.

## 18.1. Direct Access to Source Data/Documentation

The Investigator agrees by his/her participation that the results of this study may be used for submission to national or international registration. If required, these authorities will be provided with the name of the Investigator and his or her address, qualifications, and extent of involvement. It is understood that the Investigator is required to provide Sponsor with all study data, complete reports, and access to all study records.

Data generated by this study must be available for inspection by any regulatory authorities, by Sponsor, and by the IRB as appropriate. At a participant's request, medical information may be given to his or her personal physician or other appropriate medical personnel responsible for his or her welfare. Medical information obtained from participants during the course of this study is confidential and disclosure to third parties other than those noted above is prohibited.

# 18.2. Study Drug Accountability

All supplies of XT-150 study drug required for completion of this study will be provided by the Sponsor. It is the responsibility of the Investigator and study staff to ensure that a current record of drug inventory and drug accountability is maintained. Inventory and accountability records must be readily available for inspection and are open to inspection at any time by applicable regulatory authorities.

#### 18.3. Retention of Records

Essential clinical documents should be retained until at least 2 years after the last approval of a marketing application in an ICH region and until there are no pending or contemplated marketing applications in an ICH region or at least 2 years have elapsed since the formal discontinuation of clinical development of the investigational product and shipment and delivery of the drug for investigational use is discontinued. These documents should be retained for a longer period, however, if required by the applicable regulatory requirements of specific ICH- and non-ICH countries, or by an agreement with the Sponsor. The Sponsor will inform the Investigator/institution as to when these documents no longer need to be retained.

# 19. FINANCING AND INSURANCE

The financing and insurance for this study are outlined in the Clinical Trial Agreement.

# 20. PUBLICATION POLICY

The data generated in this clinical study are the exclusive property of the Sponsor and are confidential. Authorship on any publication of the results from this study will be based on

# APPENDIX 1. CLINICAL LABORATORY TESTS

## Hematology

- Hemoglobin
- hematocrit
- total and differential leukocyte count
- red blood cell count
- platelet count

# **Serum Chemistry**

- bilirubin (total and direct)
- alkaline phosphatase (ALP)
- aspartate aminotransferase (AST)
- alanine aminotransferase (ALT)

[figure not shown]

**VERSION HISTORY** 

#### 1. LIST OF ABBREVIATIONS

### Table 1:List of Abbreviations

Abbreviation	Explanation
ADaM	analysis data model
AE	adverse event
ATC	Anatomical/Therapeutic/Chemical
BMI	body mass index
bpm	beats per minute
BP	blood pressure
С	Celsius
CDISC	Clinical Data Interchange Standards Consortium
CI	confidence interval
СМН	Cochran-Mantel-Haenszel
COVID-19	coronavirus disease 2019
CSR	Clinical Study Report
CTCAE	Common Terminology Criteria for Adverse Events
DBP	diastolic blood pressure
eCRF	electronic case report form
FJOA	Facet joint osteoarthritis
HR	heart rate
ICH	International Council for Harmonization
IPAQ	International Physical Activity Questionnaire
ITT	Intent-to-treat
IWGDF	International Working Group on the Diabetic Foot
MedDRA	Medical Dictionary for Regulatory Activities
MMRM	Mixed Model for Repeated Measures
N/A	not applicable
ND	not done
SAE	serious adverse event
SAP	statistical analysis plan
SBP	systolic blood pressure
SD	standard deviation
SF12	Short Form Health Survey

### XALUD THERAPEUTICS, INC. Study Drug: XT-150

SOC	standard of care, or system organ class
TEAE	treatment-emergent AE
TFLs	tables, figures, listings,
ULN	upper limit of normal
VAS	Visual Analog Scale
WHO	World Health Organization

### 2. INTRODUCTION

This Statistical Analysis Plan (SAP) provides the framework for the summarization and analysis of the clinical data from the study, "A Placebo-controlled, Double-blind Evaluation of Safety, Tolerability, and Efficacy of XT-150 for the Treatment of Facet Joint Osteoarthritis Pain." Changes made to the SAP after it has been signed but prior to the database lock will be documented in an SAP amendment. Any important changes made to the analysis will be described in the Clinical Study Report (CSR).

### **3. STUDY DESIGN**

This is a phase 2a, randomized, double-blind, safety and efficacy study of XT-150 in adult participants experiencing back pain due to inflammation of the facet joint osteoarthritis (FJOA). Participants will receive XT-150 administered as a bilateral injection at Day 0 and Day 90, and then will be followed for safety and efficacy measures.

Up to 72 participants will be randomized 1:1:1 to placebo or one of two dose treatment groups:

- 1. 0.15 mg XT-150 (1.0mL total delivered by two 0.5 mL injections)
- 2. 0.45 mg XT-150 (1.0mL total delivered by two 0.5 mL injections)
- 3. Placebo (Sterile saline) (1.0mL total delivered by two 0.5 mL injections)

Following the first treatment with XT-150 or Placebo at Baseline (Day 0), participants will be assessed for safety and efficacy in-clinic on Days 7, 14, 30 and 60. At Day 90, participants will receive a repeat injection with XT-150 or Placebo based on treatment arm assignment at the time of randomization. Following Day 90, participants will be assessed approximately monthly through Day 270.

Participants who have passed their Day 90 visit or who were enrolled prior to the implementation of Protocol V3.0 08Jun2022 and do not reconsent to a second dose will complete the study at Day 180 and only receive the single dose at Day 0. During this visit, all End of Study visit activities should be completed.

<sup>1 The XT-150-1-0302 protocol provides XT-150 dosage levels in μg (150 μg and 450 μg XT-150), however Xalud requests dosage levels in mg. This is reflected throughout the SAP and TLF shells.

### 4. STUDY OBJECTIVES AND ENDPOINTS

### 4.1. Study Objectives

#### Primary objectives:

• To evaluate the safety and tolerability of a repeat bilateral intra-articular dose of XT-150.

#### Secondary objectives:

• To establish the analgesic efficacy of a repeat bilateral intra-articular dose of XT-150 as a treatment for pain in participants with FJOA.

#### 4.2. Study Endpoints

#### Safety Endpoints:

- Treatment-emergent adverse events (TEAE).
- Treatment-emergent serious adverse events (SAE).
- Abnormal clinical laboratory tests (chemistry and hematology).
- Vital signs (blood pressure, pulse, respiratory rate, and body temperature).
- Physical examination findings.

#### **Primary Efficacy Endpoint:**

• Change from baseline in pain intensity at Day 270 as recorded on a 0-100 VAS.

#### Secondary Efficacy Endpoints:

[figure not shown]
- Change from baseline in back disability assessed using Oswestry Disability Index (ODI) scores
- Change from baseline in Patient Global Assessment scores
- Change from baseline in International Physical Activity Questionnaire (IPAQ) scores

#### **Exploratory Efficacy Endpoints:**

- Change from baseline Short Form Health Survey (SF12) Physical Health Composite Scores (SF-12 PCS) and Mental Health Composite Scores (SF-12 MCS)
- •

5.

SAMPLE SIZE ESTIMATION

### **5.2.** Sample Size Estimation

Up to 72 participants will be randomized, 24 to each group. The sample size is not based on any formal power calculations.

### 6. ANALYSIS POPULATIONS

For purposes of analysis, the following populations are defined:

#### Table 2:Analysis Populations

Population	Description
All Participants Population	All screened participants who signed the informed consent form. Screen failure information will be summarized using the All Participants Population.
Randomized Population	All participants who met screening criteria and are randomized in the study. This population will be used to determine the other analysis populations
Intent-To-Treat (ITT) Population	All participants who were randomized who received the treatment injection and will be analyzed according to randomized treatment. This population will be used for efficacy.
Safety Population	All participants who received any amount of study drug, analyzed according to their actual treatment received. This population will be used for safety.

### 7. STATISTICAL METHODS

#### 7.1. General Considerations

#### 7.1.1. Standard Calculations

- Variables requiring calculation will be derived using the following formulas:
- Baseline: A baseline value, unless specified otherwise, is the last non-missing value recorded prior to the first dose of study drug (or placebo) on Day 0 as defined in the protocol (analysis Day 1). If an assessment has both a date and time that exactly match the date and time of first dose of study drug, the assessment will be counted as baseline.
- Change from Baseline: Change from baseline will be calculated for each participant at the specified time point as the value at the specified time point minus the baseline value.
- Study day: In the protocol, Day 0 is defined as the day of study drug administration. Subsequent study days are defined by the number of consecutive calendar days after drug administration. However, CDISC standards require the first day of study drug administration to be Day 1 and therefore, study day will be calculated differently as outlined below for display in tables, figures, and listings (TFLs):
  - Study day = date dose date + 1, where date  $\geq$  dose date
  - Study day = date dose date, where date < dose date
- Days: Durations, expressed in days, between one date (date1) and another later date (date2) are calculated according to the following formula: duration in days = (date2 date1 + 1).
- Body Mass Index (BMI): BMI (kg/m2) = weight (kg) / [[height (cm)/100]2].

#### 7.1.2. Summarization Groupings

The summary tables will be presented by randomization arm, visit, and timepoint (when applicable).

The following is a list of the abbreviations for treatment and ordering that will be used in the TFLs.

Cohort	Abbreviation for TLFS	Order on TFLs
0.150 mg XT-150	0.15mg XT-150	1
0.45 mg XT-150	0.45mg XT-150	2
Placebo	Placebo	3
Total	Total	4

radie 5: Reporting Order	Table 3:	Reporting Order
--------------------------	----------	------------------------

### 7.2. General Comments on the Statistical Analyses

- Age will be provided in the EDC as reported at Informed Consent.
- Continuous variables will be summarized using number (n), mean, standard deviation (SD), median, minimum, and maximum.
- Categorical data will be reported with frequency counts and percentages.
- Non-safety listings will be sorted by planned randomization arm, participant number, and visit in ascending order, with the exception of certain listings pertaining to screening and randomization. Safety listings will be sorted by actual treatment received, participant number, and visit in ascending order. All relevant data captured on the electronic case report forms (eCRFs) and from external laboratories including specific descriptions of 'other' and comments fields will be included on the listings.
- If a clinical laboratory result is reported relative to a lower/upper range of detection for an assay, for example, "<10", the numeric portion of the result (10) will be used for statistical analyses and the full result, including any symbols, will be provided in the participant listings.
- Analysis Data Model (ADaM) datasets will be prepared using Clinical Data Interchange Standards Consortium (CDISC) ADaM Version 2.1, and CDISC ADaM Implementation Guide Version 1.1. Pinnacle 21 Community Validator Version 3.0.1 or later will be utilized to ensure compliance with CDISC standards.
- Version 9.4 (or higher) of the SAS® statistical software package will be used to provide all tables, listings and figures.
- The analyses described in this plan are considered a priori, in that they have been defined prior to database lock. Any analyses added subsequently will be considered post-hoc and exploratory. Post-hoc analyses will be labelled as such on the output and identified in the CSR.
- Unless otherwise indicated, summaries will be performed by randomization arm.

### 7.3. Handling of Missing Data

- Unless otherwise specified, missing values for individual data points will remain as missing. Missing values will not be imputed and only observed values will be used in data analyses and presentations.
- For efficacy analyses, examining the number of participants with 30%, 50%, or 75% improvement in VAS, participants with missing data will be included in the analysis as participants who have not met the criteria for improvement.
- In all other cases, where individual data points are missing, categorical data will be summarized based on reduced denominators (ie, only participants with available data will be included in the denominators).
- Any partial dates will be presented using the CDISC standard ISO.8601 date format as shown in the SDTMIG v3.3 Section 4.4.2.

- All AEs with partial or missing dates and times will be considered treatmentemergent unless a partial start date indicates the AE began before the start of study medication or a stop date indicates the AE ended before the start of study medication.
  - For determination of treatment emergent AEs with partial start dates using the definition above, if the non-missing portion of the partial date is the same as the start of treatment or after (ex: same or later month and year), then it will be considered treatment emergent.

Ex: If treatment begins March 12th, 2022 and an AE has a partial start date of March 2022 (missing day), it will be considered treatment emergent.

- All medications with partial or missing dates recorded on the concomitant medication eCRF will be considered concomitant unless a partial stop date clearly indicates it was stopped before the first dose of study treatment.
  - For determination of concomitant medications with partial stop dates using the definition above, if the missing part of the partial date is the same (same month or year) as the start of treatment or earlier, then it will be considered treatment emergent.

Ex: If treatment begins March 12th, 2022 and a medication has a partial stop date of March 2022 (missing day), it will be considered concomitant.

	-
	-
	_

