### **10.8. Prior and Concomitant Medications**

Verbatim terms on case report forms will be mapped to Anatomical/Therapeutic/Chemical (ATC) class and generic drug name using the World Health Organization (WHO) drug dictionary, WHO Drug – Global B3, September 2021.

Prior medications are those medications started before the start of study drug. Concomitant medications are those medications taken after the start of study drug. As such, prior medications continued after the use of study drug are also considered concomitant medications. Prior and concomitant medications will be summarized for the Safety population by ATC class (level 3) and preferred term. Participants receiving the same medication more than once are counted only once for each ATC class and preferred term.

In addition, separate summaries including only back pain medication will be provided using the same format.

Prior and concomitant medications will be listed by participant, and a separate listing with medications taken for back pain will also be provided.

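### In SAP 7.3 the sub-rule for partial medication stop dates contradicts the rule it is meant to apply

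*SAP*

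**What the plan says.** SAP 7.3 (Handling of Missing Data) sets a default for medications with partial or missing dates. They "will be considered concomitant unless a partial stop date clearly indicates it was stopped before the first dose of study treatment".

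A sub-bullet, offered as the working version of that default for partial stop dates, gives this condition: "if the missing part of the partial date is the same (same month or year) as the start of treatment or earlier". Its outcome is not stated as concomitant. The sentence runs "as the start of treatment or earlier, then it will be considered treatment emergent".

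One example follows. Treatment starts on 12 March 2022 and "a medication has a partial stop date of March 2022 (missing day), it will be considered concomitant".

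The adverse-event rule just above it in the same section is built the same way but worded differently. An event with a partial start date is treatment emergent "if the non-missing portion of the partial date is the same as the start of treatment or after (ex: same or later month and year").

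SAP 10.8 supplies the governing definition: "Concomitant medications are those medications taken after the start of study drug". It plans prior and concomitant summaries in the Safety population, and then: "In addition, separate summaries including only back pain medication will be provided using the same format".

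**The concern.** The main bullet and its sub-bullet give opposite answers for the one group of records that the exception exists to handle: drugs whose incomplete stop date still shows that they ended before dosing. The main bullet excludes them and the sub-bullet takes them in.

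The sub-bullet is the more operational of the two, so it is the sentence a programmer is likely to turn into code. If that happens, a drug that ended before Day 0 stays in the prior table, which depends on its start date, and also enters the concomitant table. In a pain trial the back-pain medication summary is where a reader looks for analgesic use on study, so stopped analgesics listed there would mislead.

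**Working it through.** This is a check of logic; the plan states no figure to reproduce.

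**Inputs.** Treatment start is 12 March 2022, from the SAP 7.3 example. The rules are the main bullet and sub-bullet of SAP 7.3, with the SAP 10.8 definition as referee.

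**Making the sub-bullet codable.** Taken word for word it cannot be run. A missing day or month cannot be compared with anything, and treatment emergent is not a medication category in SAP 10.8. Two repairs are needed first: compare the part of the date that is known, and read the outcome as concomitant. The words 'or earlier' are left as they stand.

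**Rules.** Let *s* be the known part of the stop date and *t* the treatment start cut to the same precision (March 2022, or 2022 if only the year is known).
- Main bullet: not concomitant if *s* < *t*, otherwise concomitant.
- Sub-bullet: concomitant if *s* ≤ *t*; nothing is said if *s* > *t*.
- Corrected sub-bullet: concomitant if *s* ≥ *t*, prior only if *s* < *t*.

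| Partial stop date | Main bullet | Sub-bullet (repaired as above) | Corrected sub-bullet |
|---|---|---|---|
| 2021 | prior only | concomitant | prior only |
| January 2022 | prior only | concomitant | prior only |
| February 2022 | prior only | concomitant | prior only |
| March 2022 (SAP example) | concomitant | concomitant | concomitant |
| 2022, month missing | concomitant | concomitant | concomitant |
| April 2022 | concomitant | silent | concomitant |
| June 2022 | concomitant | silent | concomitant |
| 2023 | concomitant | silent | concomitant |

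**Results.** The SAP's own example comes out right under all three rules, so it cannot show which is intended. Main bullet and sub-bullet conflict in 3 of 8 cases and agree in 2 of 8. The sub-bullet says nothing in the remaining 3 of 8. The corrected sub-bullet matches the main bullet in 8 of 8.

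**Which side is wrong.** SAP 10.8 makes a drug concomitant only if it was taken after study drug began, and a drug that ended in February was not. The adverse-event rule uses the known part of the date and looks forward in time. Both agree with the main bullet.

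**The case against.** The strongest reply is that the SAP has already settled the matter. The main bullet excludes drugs that clearly stopped before dosing, SAP 10.8 does the same, and the sub-bullet says that it applies the definition above it. A programmer who must already repair two phrases to make the sentence run has the adverse-event rule close by as a model for repairing the third. This stands in part. A reader might infer that the SAP simply counts stopped drugs as concomitant, and the documents do not support that. They contain two opposed instructions, and misclassification follows only if the sub-bullet is the one coded.

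A reader might also infer that later stops, such as April 2022, are left unclassified. They are not. The sub-bullet omits them, but the default in the main bullet makes them concomitant.

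The practical reach is also limited:
- Protocol 8.5 and 9.1 ask for medications given in the month before enrollment, so most stops well before dosing should never be recorded. In the example, of the three conflicting dates only February 2022 falls within that look-back.
- Inclusion criterion 8 requires a stable analgesic regimen over the 4 weeks before enrollment, which nearly coincides with that month. Few analgesics should be both recorded and stopped earlier. Some may remain, because the criterion also admits participants who had given up analgesics for intolerance or lack of effect. It places no limit on other drug classes.
- SAP 10.8 plans by-participant medication listings and SAP 7.3 shows partial dates as partial, so the underlying dates stay visible.

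These points limit the number of affected records. They do not remove the contradiction.

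**Conclusion.** The sub-bullet is wrong as written. It contradicts its own main bullet and SAP 10.8 for every partial stop date whose known month or year precedes that of dosing, and the single example does not resolve the conflict.

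The consequence is conditional. If the sub-bullet is coded, those records appear as on-study use in the concomitant and back-pain medication summaries. Their number cannot be estimated, because the documents give no rate of partial stop dates. Any assumed rate would also overstate the effect, since partial dates in the dosing month are concomitant under both bullets and do not move.

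A reader might infer that the pain result is affected. It is not. The medication summaries are descriptive tables in the Safety population, SAP 10.8 does not pair them with the VAS analysis, and SAP 10.13 runs efficacy on the ITT population. No efficacy estimate, adverse-event rule or sample-size statement changes.

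The conclusion assumes the two repairs described in the check, without which the sub-bullet cannot be executed at all.

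**What to change.** Replace the sub-bullet in SAP 7.3 with a rule to this effect: *if the non-missing portion of the partial stop date is the same as or later than the start of treatment, the medication is considered concomitant; if it is earlier, it is prior only.* This corrects the direction, the part of the date compared and the outcome label together.

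Keep the March 2022 example and add a second that separates the rules: with the same start date, a stop of February 2022 is prior only.

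The cost is one sentence and one example, with no new data and no change to any efficacy analysis. SAP section 2 provides for an SAP amendment before database lock; after lock, the rule actually programmed should be stated in the clinical study report. A count of medications whose known stop month or year precedes that of dosing needs no treatment codes and would show how many records are involved.
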